5.6 Data Analysis

Per SPiRE protocol and discussions with an RR&D Scientific Program Manager, calculations for power and estimated effect size are not required because our proposal involves piloting a rehabilitation intervention with a small, high risk sample of VHA patients (as opposed to determining effectiveness in large samples via inferential statistical hypothesis testing).

Aim 1

Qualitative analyses of interviews from the needs assessment will be conducted with empirical phenomenological procedures used successfully by our team in previous studies.⁵⁷ Verbatim transcripts of audio recordings from the interviews will be distributed to the Co-Investigators. Each researcher will independently review, analyze, and code the transcripts for themes that characterize participants' experiences. After creating a narrative summary using the participants' own language, they will review each of their summaries to compare/contrast the identified themes before coming to consensus about important themes. A synthesized report will summarize the overarching themes.

Aim 2

WOC employees from the Program for Recovery and Community Health (PRCH) will conduct the data analysis for this aim. In line with SPIRE guidelines and recommendations for pilot studies,^{28,89} our focus will be on the feasibility of the intervention and assessment of outcomes. Therefore, quantitative analysis will be mostly descriptive in nature (e.g., frequencies, percentages, means, standard deviations) and will focus on the estimation of confidence intervals. This includes descriptive statistics on each of the measures at each assessment period, creation of confidence-intervals, and visual plotting of data to observe potential trends in the data associated with the intervention. Formal hypothesis testing will not be conducted as comparisons of outcomes would be unreliable estimates of any true effect given the small sample size. Instead, analyses will be used to evaluate the feasibility of measuring the primary outcomes and potential mediators as well as to inform decisions about power and sample sizes in a larger trial. Qualitative analyses of post-intervention interviews with Veterans will follow the same procedures as described for Aim #1. Qualitative analysis of interviews and/or focus groups with Peers Specialists conducted after completing the PREVAIL training and the pre-pilot of the intervention will also follow the same procedures as described in Aim #1.

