The PREVAIL model uses a 4-step process as a guide to their interactions with patients each of the weekly meetings: (1) Invite discussion about hope- and belongingness-related topic; (2) Learn to find out more about what participants have already tried and what participants think might be helpful or relevant to their situation; (3) Share suggestions based on their personal experience or knowledge; and (4) Motivate "change talk," including how taking action might be helpful, how they might practically go about implementing changes, and whether they have made a commitment to change. The PREVAIL model also includes having PSs "check in" midway through the 3-month intervention to gauge the patient's preference for more- or less-structured conversations or sharing, and to remind participants they are half-way through the intervention so they anticipate and prepare for termination at the 3-month point.

The second phase will involve pilot testing the feasibility and acceptability of the adapted PREVAIL, rehabilitative measures, and suicide-related outcomes for use in a rigorous prospective study. To mirror recommendations for adapting interventions and pilot studies to help prepare for larger trials,^{7,28} we will recruit 12 high suicide risk Veterans who will participate in a 3-month "pre-pilot" and provide feedback on how the

intervention may be improved. Pre-testing adapted materials and using retrospective feedback from participants are recommended steps to identifying any further changes prior to further implementation.^{7,8} After making any necessary modifications, for the third phase or 3-month “formal pilot”, we will recruit a second group of 12 Veterans who are at high suicide risk to further evaluate the feasibility and acceptability of recruitment, retention, and assessment procedures to be used in a future randomized trial. We will draw upon the support and existing resources at the VA Connecticut campuses, which house on the largest PSs programs.

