related to receiving the pilot intervention. This risk is anticipated to be minimal based on the outcomes of a R34 pilot study and ongoing R01 conducted by Co-I (developer of the PREVAIL model informing this project), where suicidal ideation improved for the whole population from baseline to 3 months, and no adverse events were attributed to study participation. Additionally, a 2018 paper² reports no iatrogenic effects from two intensive suicide research protocols involving Veterans.

Another potential risk to study participants is loss of confidentiality related to self-report assessment data, medical record data, or audio recorded sessions or interviews. The risk of an inadvertent breach of confidentiality is minimal (see below regarding protections against risk). Because of the study involves reducing suicide risk, it is necessary to obtain detailed information about past and current suicidal thoughts, plans and behaviors. Loss of confidentiality may also occur in the event that the participant is assessed by a study clinician to be imminent risk for harm to self or others therefore requiring a breach of confidentiality to ensure safety of self or others (e.g., contacting a participant's family member, law enforcement, or health care provider). Such a breach would only occur if there is no reasonably safe alternative. The informed consent process and documents will explain mandatory reporting requirements for information regarding intention to harm self or others prior to participating in the study.

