5.2 Recruitment Methods

Recruitment-Aim 1

We will recruit a diverse group of 12 individuals for the Needs Assessment phase of the project to inform the adaptation of PREVAIL. This group will be comprised of Veterans (3), Peer Specialists (3), Providers from behavioral health, inpatient and outpatient psychiatry, and other relevant departments (4), and Clinical Directors (2).

We will obtain a waiver of HIPAA authorization to identify Veterans to participate in the Needs Assessment. Once these Veterans are identified, they will be mailed a letter informing them about and requesting their participation in the Needs Assessment interviews. A member of the study team will follow-up with a telephone call approximately one week after the letter is sent. The team members will attempt to reach the Veterans by phone 3 times and will leave no more than two messages. Providers, clinical directors, and Peer Specialists will either be sent an email or will be verbally invited in person to participate in the Needs Assessment.

Recruitment for the Steering Committee

The Steering Committee will be comprised of researchers and VHA leadership. The site PI will identify appropriate VA staff and other providers and will contact them by phone or email.

Recruitment-Aim 2

We will recruit 4-6 Peer Specialists who are currently working in VA Connecticut Healthcare System (VACT) to receive training in the PREVAIL model and to deliver the intervention for the pre- and formal pilot. All of the selected Peer Specialists have been trained and certified, with multiple years of clinical experience working with Veterans in recovery, including those who have been at some point 'flagged' for suicide risk.

We will include a sample of up to 24 VHA patients identified as being high-risk for suicide at the VA Connecticut Healthcare System (VACT) to receive the pilot intervention as an adjunct to usual care. Patients will be considered high suicide risk if they have a Patient Record Flag (PRF) in their medical chart for a recent suicide attempt, serious suicidal ideation, or other warning signs of acute suicide risk. The VACT Suicide Prevention Coordinator maintains a list of patients with active PRFs. This population is targeted because they are at greatest risk for suicide and therefore most in need of intervention.

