In addition to reaching out to Veterans on the high-risk list, we also will engage Veterans via the New Haven VA psychiatric Emergency Room, inpatient units, and individual New Haven clinicians. Specifically, we will engage with staff to find out if any Veteran has received a score on the Columbia-Suicide Severity Rating Scale Screen of 3 or greater in the last three months. This measure is used commonly in the VA. Such a score is known to be an optimal cut off score for identifying individuals who would likely attempt suicide. In a recent study of nearly 19000 patients, those scoring over the cut-off of ≥ 3 had almost four times the odds of dying by suicide within 1 week and 1 month, respectively, and doubled the odds of dying within a year⁹⁰. We will also engage with individual clinicians to assess whether any of their patients have recently received a score of ≥ 3 on the Columbia measures. In addition, we will ask these staff about any Veteran who made a suicide attempt in the last three months. Thus, the additional recruitment criteria we are adding will be:

- Any Veteran from the New Haven VA psychiatric Emergency Room, the New Haven inpatient units, or from individual New Haven clinicians who received a score on the Columbia-Suicide Severity Rating Scale Screen of 3 or greater in the last three months
- Any Veteran from the New Haven VA psychiatric Emergency Room, the New Haven inpatient units, or from individual New Haven clinicians who made a suicide attempt within the last three months

Each month, there are approximately 105 VHA patients with PRFs for suicide risk at the CT VA campuses. In addition to those Veterans with a PRF, we also will be recruiting those Veterans with suicidal ideation or attempts. This pool of Veterans should be sufficient to recruit participants for the pre-pilot (n=12) and formal pilot (n=12). Assuming a 75% retention rate (as achieved in [name] PREVAIL pilot)¹⁵ this will yield a final sample of 18 patients with outcome data at post-intervention and 3-month follow-up. This sample size will yield reasonably precise estimates of feasibility in terms of actual rates of recruitment, retention, compliance/fidelity to intervention, and completion of outcome assessments.

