## Statistical Analysis Plan

Grant Title: Peer Based Suicide Prevention

ClinicalTrials.gov ID: NCT04222673

Sponsor: VA Office of Research and Development

Document date: March 8, 2022

Given the small sample size and recommendations for pilot studies, quantitative analyses were descriptive (e.g., frequencies, means) and based on the Reliable Change Index (RCI) for each participant for each outcome measure. The RCI is used to determine whether pre- to post-score differences are statistically reliable and to categorize changes as either improved, deteriorated, or indeterminate. A statistical threshold of RCI score  $z = \pm 1.96$  and  $p < .05$  was used to establish clinical significance.

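### Pre-post change in this uncontrolled pilot cannot be credited to PREVAIL, and an RCI threshold of 1.96 shows reliable change, not clinical significance

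*Protocol*

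**What the plan says.** **Design and entry.** Protocol section 5.2: "We will include a sample of up to 24 VHA patients identified as being high-risk for suicide", all to receive the intervention in addition to usual care. Section 5.1 describes two cohorts in sequence, a pre-pilot of 12 and then "we will recruit a second group of 12 Veterans who are at high suicide risk". Neither cohort has a comparison group. Entry is by a Patient Record Flag (placed for an attempt, serious ideation or acute warning signs), or, under section 5.2, by a C-SSRS Screen score of 3 or more, or an attempt, in the last three months.

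**Concurrent care.** Section 2.0 says that flags stay in place for at least 90 days and require at least four clinical contacts in the first 30 days after flagging or discharge. Section 5.1 sets the three-month intervention to match the typical life of a flag.

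**Analysis.** Section 5.6 calls the quantitative analysis mostly descriptive and rules out formal tests, because outcome comparisons would be unreliable in so small a sample. It plans "visual plotting of data to observe potential trends in the data associated with the intervention" and says the analyses will also serve "to inform decisions about power and sample sizes in a larger trial". The SAP uses the RCI on each outcome measure to "categorize changes as either improved, deteriorated, or indeterminate", with z = ±1.96 and p < .05 as the mark of clinical significance.

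**Earlier experience.** In discussing risk, section 5.1 reports that in the developer's earlier PREVAIL work "suicidal ideation improved for the whole population from baseline to 3 months".

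**The concern.** People recruited because of a recent crisis tend to look better three months later whatever is done, and these participants are also receiving usual care for that crisis. Without a comparison group, the plan cannot tell such change from an effect of PREVAIL. The one stated caveat, sample size, does not help: a single-arm study of any size would carry the same bias.

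The RCI does not remove the problem. It asks whether a person's change exceeds what measurement error would produce if the expected change were zero. It makes no allowance for an expected improvement without treatment, and it does not judge whether a change matters to the patient.

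For some participants a fall in suicidal behavior is partly built in. The C-SSRS behavior window in section 5.5 is three months, and an attempt in the last three months is an entry route, so the qualifying attempt can be counted at baseline.

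At stake is what the pilot may conclude. A table of improved participants labelled clinically significant, beside plots of trends tied to the intervention, would invite a reading of benefit that the design cannot support, in a study meant to inform a multi-site randomized trial.

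**Working it through.** **1. The plan's own figure.** Section 5.2: "Assuming a 75% retention rate", "this will yield a final sample of 18 patients with outcome data at post-intervention and 3-month follow-up". 24 × 0.75 = 18, which reproduces. No power, effect size, SD, reliability or retest correlation is given, so everything in steps 2 to 4 is assumption.

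**2. The RCI cut.** In SD units, with R the reliability used in the RCI, a participant is classed as improved if the change exceeds k = 1.96 × √(2(1 − R)). R = 0.90 gives k = 0.877; R = 0.70 gives 1.518; R = 0.60 gives 1.753.

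**3. Regression only, no intervention effect.** Let entry lie e SDs worse than the person's usual population mean, and let r be the three-month retest correlation. Expected improvement is (1 − r)e, with SD √(1 − r²), so

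P(improved) = 1 − Φ((k − (1 − r)e) / √(1 − r²)).

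| RCI reliability R | r | e = 0 | e = 1 | e = 2 |
|---|---|---|---|---|
| 0.90 | 0.7 | 11.0% | 21.0% | 34.9% |
| 0.90 | 0.6 | 13.7% | 27.6% | 46.2% |
| equal to r | 0.7 | 1.7% | 4.4% | 9.9% |
| equal to r | 0.6 | 1.4% | 4.5% | 11.7% |

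Example, R = 0.90, r = 0.6, e = 2: (0.877 − 0.8)/0.8 = 0.096, giving 46.2%, or 8.3 of 18.

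The e = 0 column matters. With R = 0.90 and no regression at all, 11.0% to 13.7% are classed as improved and the same share as deteriorated, purely because the assumed reliability exceeds the retest correlation. Regression adds the asymmetry: at e = 2 only about 2% are classed as deteriorated.

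**4. Any non-specific shift.** If recovery, care and regression together move the mean by d baseline SDs, then P(improved) = 1 − Φ((k − d) / √(2(1 − r))).

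| R | r | d = 0 | d = 0.5 | d = 0.8 |
|---|---|---|---|---|
| 0.70 | 0.70 | 2.5% | 9.4% | 17.7% |
| 0.90 | 0.90 | 2.5% | 20.0% | 43.2% |
| 0.90 | 0.70 | 12.9% | 31.3% | 46.1% |

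Across 18 completers, 2.5% is 0.45 people and 46.1% is 8.3. In the second row regression is not the main cause: at r = 0.90, entry 2 SD worse regresses by only (1 − 0.9) × 2 = 0.2 SD, so the rest of d would have to be recovery or care.

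**5. Dependence on timing.** A simulation that selected on a crisis screen score gave no net shift when the screen correlated equally (0.5) with the baseline and follow-up scores, that is, when the crisis had subsided by baseline. With a screen-baseline correlation of 0.90 to 0.95, that is, baseline close to the crisis, 45% to 72% were classed as improved when the RCI used the selected sample's SD, and 25% to 53% when it used the unselected population's SD. The documents do not fix the interval from crisis to baseline.

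**6. Precision of an SD passed forward.** With 17 degrees of freedom, the 95% limits are √(17/30.19) = 0.75 and √(17/7.564) = 1.50 times the estimate. Required sample size scales with SD², so it is uncertain by a factor of 0.56 to 2.25. This holds for any pilot of this size and is secondary here.

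**The case against.** The strongest reply is that the plan is already modest. It disclaims hypothesis testing, calls its analyses descriptive, bases progression on more than 50% enrollment and more than 70% follow-up completion (Protocol abstract), and names a randomized trial as the next step. RCI counts decide nothing. This stands, and it limits the severity. It does not remove the attribution in section 5.6 or the label in the SAP.

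Three stronger readings are tempting, and the documents do not support them.

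- *Many participants will be falsely classed as improved.* Selection is on a flag, a screen score or an attempt that may be three months old or more, not on the baseline outcome scores, and most outcome measures are not selection variables. The mandated contacts of the first 30 days may also precede baseline. The excess could be large or close to nothing.
- *The plan reads the RCI classes as effects of PREVAIL.* The trend wording in section 5.6 concerns plots and is tentative. The SAP attributes its classes to nothing.
- *The next trial will be underpowered because pre-post change will be its effect size.* Section 5.6 does not name the quantity carried forward, and SDs, correlations and retention are legitimate inputs. If an uncontrolled change of 0.8 or 0.5 SD were used (80% power, two-sided 0.05), the trial would have 25 or 63 per arm, and 18% or 39% power for a true effect of 0.3 SD. No passage says this will be done; none excludes it.

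The remark that ideation improved in the earlier work is a safety statement, not a claim of efficacy. It does show that improvement over three months can be expected across a whole study population.

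**Conclusion.** The point holds on the text and needs no assumed parameter. A single-arm sample chosen by recent suicide risk and treated alongside usual care cannot support trends tied to the intervention, and a caveat about sample size does not cover bias. Separately, the SAP's label contradicts its own description of what the RCI measures.

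The size is not known. With no intervention effect, the share classed as improved runs from near the nominal 2.5% to over 40%, depending on reliability, retest correlation, non-specific shift and the timing of baseline, none of which the documents give. Where the assumed reliability exceeds the retest correlation, part of the upper figures comes from that mismatch.

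Severity is minor to moderate: what the pilot may conclude is affected, but the decision to progress is not.

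**What to change.** 1. **SAP:** change the stated purpose of the ±1.96 threshold from establishing clinical significance to classifying change as statistically reliable. Give the reliability and SD used in the RCI for each measure.
2. **Protocol section 5.6:** describe the plotted trends as trends over time, without linking them to the intervention.
3. **Both documents:** state that RCI counts and pre-post changes are uncontrolled and are not attributed to PREVAIL, naming regression to the mean, natural recovery and concurrent care as reasons. Note that the baseline C-SSRS behavior window can include the qualifying attempt.
4. **Section 5.6 (clarification):** state that only recruitment and retention rates, SDs with 95% confidence intervals, and pre-post correlations will inform the next trial's sample size, and that the pre-post change and the RCI improvement rate will not.

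The cost is a few sentences and one confidence interval per measure, with no change to design or data collection. The downside is a weaker statement of preliminary efficacy.

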5.7 Withdrawal of Subjects

As discussed in Section 5.1 of the protocol, the risk of clinical deterioration of mental health and/or an increase in suicidal thoughts or behaviors related to receiving the pilot intervention is anticipated to be minimal, therefore we believe that few participants will need to be terminated. Participants who are hospitalized during the project will not be withdrawn, but the intervention will continue, either during their stay if medically appropriate, or following their discharge.

If study staff becomes aware of Veterans who are incarcerated and/or become pregnant during the study period, the Veteran will be withdrawn from the study. Other potential reasons for withdrawal include if a participant relocates out of state or misses the first four scheduled sessions. Any participant may withdraw from the study at any time, as stated in the ICF. If a participant calls the research staff to withdraw, the staff member

will thank the Veteran for their participation and ask whether the Veteran would like to schedule a behavioral health appointment related to their study participation or decision to withdraw. A note will be added to the Veteran's medical record indicating their decision to withdraw, and the behavioral health provider of record will be informed.

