The PREVAIL intervention consists of weekly interactions over the course of 3-months using a flexible approach to accommodate Veteran's preferences and recovery needs over the course of the typical duration of a PRF. During weeks 1 and 2 of the intervention, Veterans meet twice weekly with a PS. During weeks 3 through 8, meetings are once weekly. During weeks 9 through 12, meetings typically occur once every other week. Over the course of the 3-month intervention, this approach bolsters the development of a strong therapeutic alliance in the beginning (weeks 1-2), followed by active teaching and reinforcing new skills (weeks 3-8), and then culminating with mastering new skills and preparing the Veteran for active self-management and sustained recovery. For a small number of PREVAIL participants, an additional 3 sessions were added over the span of the last 4 weeks to provide additional time to prepare for the end of the therapeutic relationship. A similar approach will be used for the current pilot.

Meetings between PSs and Veterans will be approximately 45-60 minutes and occur primarily in the community, home, clinic, by telephone, or VA-approved video calling platform (e.g. VVC, WebEx). Session content will be rooted in PSs offering nonjudgmental empathic support, active listening, and constructive disclosure and role modeling. A primary focus will be helping patients with PRFs to identify and strengthen connections with informal supports and participation in activities in their community that will enable them to feel more worthwhile as individuals and hopeful about their future.

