Veterans in both the pre-pilot and formal pilot will each meet with research staff for a Baseline Visit, Post-Intervention Visit, and a 3-Month Follow-Up Visit. All participants will also be invited to participate in an in-depth qualitative interview shortly after their 3- month follow-up assessments to assess their views of the intervention, including barriers, strengths, and recommended changes. All qualitative interviews will be recorded and transcribed. During the interviews, participants will be encouraged to avoid using names. If any name is recorded, it will be omitted from the written transcript (i.e., the transcript may read [name] in place of the actual name). Only the study team will have access to data collected by questionnaires, interviews, and medical record data.

Risks and Risk Minimization

Needs Assessment (Aim 1): There are no foreseeable physical or medical risks in this portion of the project. However, potential participants will be informed of the general nature of the study, what their involvement entails, the risks/benefits, and limitations to confidentiality prior to providing informed consent. The site PI for VA Connecticut and Co-I will contact key staff and make arrangements for interviews. Three Veterans will be identified pursuant to a HIPAA waiver, and a letter will be mailed to them inviting their participation.

We will minimize risks to interview participants by thoroughly explaining to them that participation in the project is strictly voluntary and that the decision not to participate will have no bearing on their employment. Individual names of employment settings and associated responses will not be provided to any other agency. In reports, publications, or presentations using project research data, we will report the data in aggregate form and/or change names and disguise the identity of any individual we describe or quote for purposes of illustration or example.

Pre-and Formal Pilot Testing (Aim 2): A potential risk to study participants is clinical deterioration of their mental health and/or an increase in suicidal thoughts or behaviors

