Based on the level of risk determined by the algorithm, study staff may perform one or more of the following. In the presence of elevated acute suicide risk, several steps will be taken to ensure participant safety (See Appendices A and B). First and foremost, should the participant disclose suicidal plan and/or intent OR recent suicidal behavior (e.g., suicide attempt or preparatory behavior in the past month) then the peer specialist or research assistant will conduct a warm hand off to a licensed mental health provider to further assess and intervene as appropriate (e.g., Safety Planning, hospitalization). Similarly, should the participant report these factors during a research interview on a self-report assessment (e.g., QIDS or C-SSRS), a warm hand off to a licensed mental health provider will be conducted. For lower, non-acute risk, steps taken by study staff include: a) recommend the participant call or be transferred to the Veteran Crisis Line or the VHA Psychiatric Emergency Services b) notify the participant’s primary Mental Health clinician and/or Suicide Prevention Coordinator regarding a non-imminent increase in suicide risk. When any suicidal ideation is reported, study staff will c) notify a designated on-call study team clinician when the suicide risk management algorithm has been activated, and when any questions arise regarding risk management. The on-call study clinician will be available via pager or cell phone at all times when there is potential contact between study staff (including peer specialists) and participants. Additionally, health and social service resources will be provided to the participant. This will include several resources, including suicide prevention resources which the participant can access. This will facilitate and enhance care on an ongoing basis among

this population.

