Once eligible Veterans are identified, they will be mailed a letter along with a study information sheet, inviting them to participate in Aim 2 of study. A member of the study team will follow-up with a telephone call approximately one week after the letter is sent if they do not hear back from the Veterans. The team members will attempt to reach

the Veterans by phone 3 times and will leave no more than two messages.

Additionally, the site PI will work with providers of eligible Veterans seeking their help in recruiting these Veterans into the study and will also provide them with a study information sheet. Once the provider identifies an eligible Veteran, they will discuss the study with the Veteran and if the Veteran is interested in hearing more about the study, the provider will call the study staff with the Veteran present or will share the number of the study staff with the Veteran so that they may call the study staff at their own convenience. In the event that the provider facilitates the phone call with study staff, the provider will step out of the room to give the Veteran a chance to learn more about the study. for this to occur. If a provider or research staff cannot reach the Veteran by phone, they will follow-up with a CIRB-approved letter as described above.

Version 4.0 Suicide Prevention Protocol Page **20** of 36

Payments

Veterans who participate in the Needs Assessment interview will receive \$25 for their time and effort. Study participants will receive \$25 upon completion of each assessment interview (baseline, post-intervention, 3-month follow-up), for a total of up to \$75. Additionally, Veterans who participate in the one-time interview will receive \$25 for their time and effort.

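### Missing the first four sessions may withdraw a Veteran from the study, and no available text says that such a Veteran is still assessed

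*Protocol*

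**What the plan says.** Protocol Section 5.7 first says that Veterans who are incarcerated or become pregnant are removed from the study. It continues: "Other potential reasons for withdrawal include if a participant relocates out of state or misses the first four scheduled sessions". The steps it describes at withdrawal are thanks and the offer of a behavioral health appointment for a participant who calls to withdraw, a note in the medical record, and informing the behavioral health provider. It mentions no further assessment and no exit interview. The same section explicitly keeps hospitalized participants in the study.

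The default for pilot Veterans is in Section 5.1: they "will each meet with research staff for a Baseline Visit, Post-Intervention Visit, and a 3-Month Follow-Up Visit". All participants are also to be invited to an "in-depth qualitative interview shortly after their 3- month follow-up assessments to assess their views of the intervention".

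Section 5.2 (Recruitment-Aim 2) says that the sample should inform "feasibility in terms of actual rates of recruitment, retention, compliance/fidelity to intervention, and completion of outcome assessments". From 24 Veterans at 75% retention, it expects that "this will yield a final sample of 18 patients with outcome data at post-intervention and 3-month follow-up". The Abstract sets the feasibility criterion at more than 70% of enrollees completing follow-up assessment.

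The SAP classifies each participant on each measure by a Reliable Change Index (RCI), computed from pre and post scores. It does not mention withdrawal, missing data or the analysis population.

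**The concern.** The ground appears under the heading on withdrawal of subjects, directly after a sentence about leaving the study. Its natural reading is withdrawal from the study and not only from sessions. Nothing available for review separates the two.

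If staff use the ground, a Veteran who never takes up the sessions may leave with baseline data only. Three things follow:

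- No RCI category can be assigned, because there is no post score.
- The Veteran counts as a non-completer in the feasibility rate, even if willing to be assessed.
- The participant interview is out of reach, because it is scheduled after the 3-month assessment.

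This matters because Aim 2 is about feasibility and acceptability. Section 5.2 treats compliance with the intervention and completion of assessments as two separate rates, but this ground lets the first affect the second. The Veterans concerned are also the ones who could best describe early barriers to taking up the intervention.

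**Working it through.** **Inputs.** Planned enrolment is 12 + 12 = 24 and assumed retention is 75% (Section 5.2, Recruitment-Aim 2). The feasibility criterion is more than 70% of enrollees (Abstract). The session schedule is in Section 5.1.

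**Step 1: the plan's own figure.** 24 × 0.75 = 18 with outcome data, so 24 − 18 = 6 are lost from all causes. The stated 18 is reproduced.

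**Step 2: what the criterion needs.** 0.70 × 24 = 16.8, so at least 17 of 24 must complete (17/24 = 70.8%). The margin over the plan is 18 − 17 = 1 person.

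**Step 3: the weight of one Veteran.** 1/24 = 4.2 percentage points.

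**Step 4: further losses.** Assume that k Veterans who would have been assessed are withdrawn on this ground, on top of the planned loss. All 24 stay in the denominator, as the Abstract's reference to enrollees implies.

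| k | Completers | Rate | Above 70%? |
|---|---|---|---|
| 0 | 18/24 | 75.0% | yes |
| 1 | 17/24 | 70.8% | yes |
| 2 | 16/24 | 66.7% | no |

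If these Veterans are instead already among the 6 expected losses, the planned rate stays at 75.0%, and each one who is still assessed raises it by 4.2 points (19/24 = 79.2% for one). The documents do not say which case applies or how many Veterans are affected.

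**Step 5: when the ground can be met.** Section 5.1 states: "During weeks 1 and 2 of the intervention, Veterans meet twice weekly with a PS". On that schedule 2 × 2 = 4 sessions fall in weeks 1 and 2, so the ground could be met by the end of week 2. The Data Safety and Monitoring plan, also in Section 5.1, describes one visit per week, which puts it at about four weeks. The two passages must be reconciled. On either, the ground can be met well before the post-intervention visit that follows the 3-month intervention.

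**Step 6: other sources of information.**

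- Section 5.1 plans a second Peer Specialist focus group after the pre-pilot, with possible individual interviews. It could report early non-engagement, but second-hand.
- The three Veterans interviewed for Aim 1 are seen before the pilots and not as recipients.
- The Abstract plans a chart review at 3-month follow-up. Whether it covers withdrawn Veterans is not stated.

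**The case against.** The strongest reply is that the loss is only conditional. The protocol calls these potential reasons, its default is that every pilot Veteran attends all three visits, and all participants are invited to the interview. Harm requires a Veteran who misses four sessions, is then withdrawn, is then not assessed, and would have come to an assessment. No frequency is given for any of these steps. This stands, and it rules out reading the ground as automatic. It does not remove the gap, because the default visits are for those still in the study and Section 5.7 is silent on what follows withdrawal.

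Second, the results in the table with k above 0 assume losses beyond the planned 25%. Early non-attenders may already be within it. This also stands. The thin margin is moreover not specific to this ground: any other extra loss moves the rate equally, and the exact 95% interval for 18/24 is 53.3% to 90.2%.

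Third, the study is single-arm and descriptive, without hypothesis testing, and the pre-post change of someone who attended no session says little about the intervention. This largely stands for the RCI. What remains is that the RCI counts would describe a selected group without saying so, and that completion of assessments is itself a feasibility outcome.

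Two stronger readings are tempting:

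- A reader might infer that withdrawn Veterans drop out of the denominator and so flatter the rate (16/22 = 72.7% in place of 16/24 = 66.7%). The Abstract's denominator is enrollees, so the text points the other way.
- A reader might apply the 70% rule to each group of 12, where the planned 9/12 = 75.0% leaves no margin and 8/12 = 66.7% fails. No passage applies it there, and Section 5.2 pools to 24.

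Finally, the consent form and some protocol pages are not available and may address assessment after withdrawal. The conclusion is limited to the text available.

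**Conclusion.** The point holds in a conditional form. If the ground is used, session non-attendance ends outcome assessment. The early non-engagers' own views and outcomes may be lost, and the feasibility rate partly reflects attendance and not willingness to be assessed. The error is towards a false conclusion that the study is not feasible.

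The size is unknown because the documents give no expected number. Each affected Veteran who would have been assessed is worth 4.2 points on 24. The plan can absorb one such loss beyond the 6 expected, but not two. This rests on two assumptions: such losses are additional to the planned 25%, and the denominator is all 24 enrollees.

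A reader might infer that the pilot will fail its criterion because of this ground, or that its results are biased in favour of the intervention. The documents support neither. The change is worth making as an inexpensive improvement to the plan.

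**What to change.** None of this changes when sessions stop, and whether the session rule itself is right is not judged here.

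1. In Section 5.7, separate stopping the intervention from leaving the study. A Veteran who misses the first four sessions, has not withdrawn consent and meets no other withdrawal ground should still be invited to the post-intervention and 3-month assessments and be included in the chart review, subject to the consent form.
2. Offer these Veterans the existing one-time interview at the time sessions stop, without waiting for the 3-month assessment.
3. In the SAP, report the number without a post score beside the RCI counts.
4. Reconcile the two statements of session frequency in Section 5.1, since they determine when the ground can be met.

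The cost is protocol and consent wording, some extra effort to contact non-attenders, and use of the existing risk-management procedures at those visits. Those procedures already provide that, where a participant reports a suicidal plan, intent or recent behavior at a research assessment, "a warm hand off to a licensed mental health provider will be conducted". No new payment type is needed. Section 5.2 (Payments) already provides $25 for each assessment, and for the interview it says "Additionally, Veterans who participate in the one-time interview will receive" a further $25. The SAP is written in the past tense, so items 1 and 2 may come too late for this cohort. Item 3 could still be done, and the separation in item 1 can be carried into the planned randomized trial.
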